**Healthy Controls:**

1. M/F, 18-50 y/o, age  $\pm$  3y sex, race, and BMI ( $\leq$  3 kg/m^2) match with UC subject
2. No clinical evidence of any medical illness
3. Normal psychological evaluation based on question responses and negative drug screen (See Below)

**Ulcerative Colitis:**

1. M/F, 18-50 y/o.
2. Inactive Disease (Mayo Score  $\leq$  2)
3. Stable medications with no disease flares for the > 3 months
4. Left-sided UC (Montreal E1 or E2)
5. Normal psychological evaluation based on questionnaire responses and negative drug screen (See Below)

**Exclusion Criteria:** *Study will not include individuals that are;*

**Healthy Controls**

1. History of drug abuse, gastrointestinal (GI) surgery, GI diseases, or systemic diseases such as renal (creatinine $>1.2$  mg/dl), liver, cardiac, or diabetes (Hgb-A1c $>8\%$ )
2. Antibiotic use within last 12 weeks
3. Shift work in the last 6 months
4. Use of probiotic supplement except yogurt in last 4 weeks.
5. Atypical American diet with daily fiber  $\geq 16$  grams or daily saturated fat  $\leq 11$  grams by Food Frequency Questionnaire
6. Chronic use of NSAIDS. A washout period of 3 weeks is needed before the subject could be enrolled into the study.
7. Chronic Alcohol use. A washout period of 3 weeks is needed before the subject could be enrolled into the study.
8. Significant Depression (score  $\geq 14$  BDI)
9. Significant Anxiety (score  $\geq 40$  STAI)
10. Regular use of medications that affect intestinal permeability, intestinal motility and/or endogenous melatonin including metoclopramide, NSAIDs, antibiotics, beta blocker, psychotropic medication, hypnotics and exogenous melatonin products during 4 weeks prior to the study
11. People who crossed more than 2 time zones in the previous month
12. Inability to sign an informed consent form.
13. Have children Under 6 Months

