prevalence of shift work, and nighttime eating have made misalignment of our endogenous circadian rhythms more common. There are multiple causes for human circadian misalignment including shift work, long distance travel with jet lag, and perhaps the most common: social jet lag, which is changing the midpoint of sleep more than 2h between work and work-free days due to social obligations. The most well-studied model of circadian misalignment, shift work, is now estimated to include 15 million workers in the US. Not surprisingly, shift work is associated with a number of GIT disorders and diseases including irritable bowel syndrome, peptic ulcer disease, and colon cancer. Therefore, it is possible that circadian misalignment may be one factor that promotes intestinal inflammation and disease flare in UC.

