In addition, subjects will provide basic demographic data, UC history if appropriate, UC disease activity status as detailed further above, and the Munich Chronotype questionnaire. All subjects will complete a validated 3-month food frequency questionnaire (FFQ) to collect dietary information (1). 40 participants (Specific Aims 1-2) will be enrolled for the within-subject prospective in-laboratory study protocols. Participants will be young (18-50 y), healthy, non-diabetic, non-obese, Caucasian/African American/Asian and non-Hispanic/Hispanic in ratios consistent with the population of Chicago, and without medication use (excepting oral contraceptives) for HC. HC and UC subjects will be matched according to age ( $\pm 3$  years), sex, race, and BMI ( $\pm 3$  kg/m^2). UC subjects will be on stable medications with no recent use of prednisone or antibiotics for the last 3 months. After signing an informed consent, the subject will fill out questionnaires, start a food diary, and sleep diary, and have 2 weeks of wrist actigraphy before their seven-day in lab session in the Clinical Chronobiology Center (CCC). Since participants will be in the sleep lab for 7 days and isolation can cause an increase in depression and anxiety, a normal psychological evaluation is part of the inclusion criteria for this study. This will be determined based on how participants respond on the BDI and STAI questionnaires, which assess depression and anxiety. The study physician will review the questionnaire responses and evaluate if the participant will feel comfortable staying in the lab for 7 days.

**Subject Characteristics:** We will recruit (1) 20 HC subjects without any medical illnesses (2) 20 subjects with biopsy proven UC, inactive (Mayo Score  $\leq 2$ ) on stable medications and no disease flares for  $> 3$  months. HC and UC subject will be matched according to age ( $\pm 3$  years), sex, race, and BMI ( $\pm 3$  kg/m^2).

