**Ulcerative Colitis:**

1. Patients with other forms of colitis such as Crohn's disease (CD) or indeterminate colitis
2. Patient with active UC (Mayo  $> 2$ )
3. Pancolonic UC (colitis past the splenic flexure, Montreal E3))
4. Gastrointestinal surgery
5. Other GI diseases or systemic diseases (cardiac, renal failure, cirrhosis)
6. Shift work in the last 6 months
7. Antibiotic use within last 12 weeks
8. Patients who have used anti-diarrheal agents such as Lomotil or Imodium within 3 days of the study
9. Prednisone use the last 30 days
10. Significant Depression (score  $\geq 14$  BDI)
11. Significant Anxiety (score  $\geq 40$  STAI)
12. Use of probiotic supplement in last 4 weeks except yogurt.
13. Intentional change in diet.

14. Chronic use of NSAIDS. A washout period of 3 weeks is needed before the subject could be enrolled into the study. Low dose aspirin is allowed.
15. Chronic Alcohol use. A washout period of 3 weeks is needed before the subject could be enrolled into the study.
16. Have children under 6 months

**Subject Recruitment:** All Human UC subjects will be recruited at the RUMC Digestive Disease Clinic and the Rush Crohn's and Colitis Center by the PI or Clinical Coordinator. Healthy control subjects will be recruited by established recruiting methods, which we have successfully used over the past ten years, including notices to local organizations and internet, newspaper, and radio advertising. Based on our experience, of the initial calls made by potential subjects, 15% remain interested in the study after they are informed of study procedures. Of these individuals, 70% pass an initial telephone screening (in which questions are asked about medical condition, current medication use and work and travel history). Of those remaining individuals, 33% pass the medical and psychological screening (described below), and of these, 70% complete the study.

In this study we will recruit 40 Human Subjects in the following two groups:

- 1) Ulcerative Colitis (UC) (n=20).
- 2) Healthy Controls (HC) (n=20).

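### The time-zone exclusion is written for healthy controls only, so the baseline UC-versus-control phase-angle contrast may carry a small, avoidable bias

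*Combined protocol and SAP*

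**What the plan says.** **Travel.** Exclusion Criteria, Healthy Controls, item 11 excludes "People who crossed more than 2 time zones in the previous month". None of the 16 items in the UC list mentions travel. The other circadian exclusion, recent shift work, is in both lists (control item 3, UC item 6). Background A.2 states: "There are multiple causes for human circadian misalignment including shift work, long distance travel with jet lag". Under Subject Recruitment, at the telephone stage "questions are asked about medical condition, current medication use and work and travel history".

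**Medication.** Control item 10 excludes "Regular use of medications that affect intestinal permeability, intestinal motility and/or endogenous melatonin including metoclopramide" and six further drugs or classes, over four weeks. The UC list has its own items for antibiotics (item 7) and chronic NSAIDs (item 14), and one for "Patients who have used anti-diarrheal agents such as Lomotil or Imodium within 3 days of the study". It names none of the other five: metoclopramide, beta blockers, psychotropics, hypnotics and melatonin products. For all subjects, the Diet Assessments paragraph prohibits prescribed drugs subject to exceptions it does not list, and bars other compounds for three weeks with a toxicology check. Minimizing Risk, item 6, excludes any psychiatric history.

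**Diet.** Control item 5 ("Atypical American diet with daily fiber" and saturated-fat limits from the food frequency questionnaire, FFQ) has no UC counterpart. The only diet item in the UC list is item 13, on deliberate dietary change.

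**The contrast.** Aim 1 asks whether misalignment is commoner in UC than in controls. Its primary measure is phase angle (melatonin onset to sleep onset), with ANOVA named in Figure 1. Matching is on age, sex, race and BMI, and Sample Size Analysis names order effects as the only covariate.

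**The concern.** A rule that screens a known cause of misalignment out of one group only is differential selection on the outcome. UC subjects who recently crossed several time zones may be enrolled; controls who did so may not. Any displacement left at the baseline assessment would then enter the UC-minus-control difference. Neither the matching nor the named covariate would remove it. The documents do not say which way travellers would be displaced, so the direction of the bias is unknown.

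The same reasoning applies, more weakly, to drugs acting on endogenous melatonin, because the primary measure is timed from melatonin onset. Nothing about the disease or its treatment explains leaving travel off the UC list. That shift work appears in both lists suggests an oversight.

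**Working it through.** **1. How much of the month is already covered.** All subjects hold a fixed sleep schedule for 2 weeks before the phase assessment (Procedures), with wrist actigraphy. Taking a month as 30 days, 30 - 14 = 16 days are uncovered. Data Analysis Methods gives 3 weeks of actigraphy instead; on that reading 30 - 21 = 9 days are uncovered. Either way the uncovered days are the earliest ones.

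**2. Inputs from the plan.** Sample Size Analysis gives 20 per group, two-sided alpha 0.05, and melatonin-onset means of -0.2 h (SD 2.1) and -4.34 h (SD 3.8). The difference is 4.34 - 0.2 = 4.14 h, and the pooled SD is sqrt((2.1² + 3.8²)/2) = 3.07 h. A two-sample t-test on these gives 98.6% power, which reproduces the printed 98%. These SDs come from night and day workers; here they stand in for the SD of phase angle in UC subjects and controls.

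**3. Assumed inputs, not in the documents.** Let m of 20 UC subjects be displaced by r hours, all in the same direction, with no true group difference. The UC mean then moves by m × r / 20:

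- m = 1, r = 3: 1 × 3 / 20 = 0.15 h
- m = 2, r = 3: 2 × 3 / 20 = 0.30 h, or 0.30 / 3.07 = 0.10 SD
- m = 4, r = 3: 4 × 3 / 20 = 0.60 h, or 0.60 / 3.07 = 0.20 SD

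**4. False-positive rate.** Displacing only some subjects also inflates the UC variance, so the rate was simulated: 60,000 trials per cell, 20 versus 20, two-sided t-test (equivalent to a two-group ANOVA).

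| m of 20 | r (h) | SD 2.1 | SD 3.07 | SD 3.8 |
|---|---|---|---|---|
| 1 | 3 | 4.9% | 4.9% | 5.1% |
| 2 | 3 | 6.1% | 5.6% | 5.3% |
| 4 | 3 | 10.9% | 8.0% | 6.9% |
| 2 | 6 | 7.9% | 6.8% | 6.3% |

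Simulation error near 5% is about sqrt(0.05 × 0.95 / 60,000) = 0.09 percentage points, so the first row cannot be told apart from 5%. With 2 of 20 displaced by only 1 h the rate is 5.0-5.1%. Mixed directions, or recovery during the monitored weeks, would lower every row.

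**5. Medication rules side by side.** Of the seven drugs or classes in control item 10, two have UC items and five do not. The study-wide rules reach most of those five, but the exceptions are not stated in one place: Data Analysis Methods describes UC treatment as aminosalicylates, while the Blood draw paragraph provides for patients on biologics. The windows also differ: four weeks in item 10 and three in Diet Assessments.

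**The case against.** The strongest reply is that two weeks on a monitored schedule should remove most carry-over. Minimizing Risk, item 5, likens readjustment after the study to jet lag and expects it to take several days. That is not a measurement of melatonin-onset recovery, but it is the only timescale the documents give, and it makes residual shifts of 3-6 h doubtful. The protocol also describes itself as within-subject, and stable differences largely cancel in the baseline-to-misalignment change. Both points stand, and they are why this is minor. They do not remove the one-sided rule or the between-group question in Aim 1.

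A reader might also infer four stronger things that the documents do not support:

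- *That the baseline contrast is confounded.* No imbalance in travel is shown, and its frequency is not given. The supported wording is that it may be.
- *That UC subjects may freely take the five unlisted drugs.* The prohibition on prescribed drugs, the toxicology check, and the cardiac (UC item 5) and psychiatric exclusions leave little room. The remaining fault is an unlisted set of exceptions.
- *That the FFQ asymmetry biases phase angle.* The documents justify diet exclusions by the microbiota, and Background A.2 ties high-fat diet to a mismatch between central and peripheral clocks, not to phase angle.
- *That the aspirin statements conflict.* "Low dose aspirin is allowed" is in the UC list, whereas "without medication use (excepting oral contraceptives) for HC" concerns controls. They apply to different groups.

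**Conclusion.** The asymmetry is real and minor. As written, recent travel across more than 2 time zones excludes a control but not a UC subject, and the baseline phase-angle contrast may carry a small bias of unknown direction. Under same-direction shifts of 3 h, the false-positive rate is essentially 5% with 1 of 20 UC subjects affected, 5.3-6.1% with 2, and 6.9-10.9% with 4. These figures rest on assumed numbers and shifts, and on melatonin-onset SDs standing in for phase angle. The within-subject change is less exposed.

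The medication rules need reconciling rather than a new restriction. The FFQ asymmetry bears on microbiota and other Aim 2 secondary outcomes where groups are compared; its size cannot be derived from the documents.

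**What to change.** 1. Apply the time-zone exclusion to both groups.
2. Reconcile control item 10, the UC exclusion list, Diet Assessments and Data Analysis Methods into one common criterion for drugs affecting melatonin, with a single stated window and the permitted UC exceptions listed. Which exceptions and which window is for the investigators to settle.
3. For diet, use the same FFQ criterion in both groups, or examine FFQ intake in the between-group analyses of microbiota and other Aim 2 secondary outcomes.

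No sensitivity analysis for aspirin use and no FFQ-restricted analysis of phase angle is needed.

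The cost is eligibility wording. Travel and medication history are already asked at telephone screening, and all subjects complete the FFQ. The downside is a slightly smaller UC pool. The documents give no travel frequency from which to compute the loss, but the rule looks back only one month, so a recent traveller could be admitted later.

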**Ulcerative Colitis:**

1. Patients with other forms of colitis such as Crohn's disease (CD) or indeterminate colitis
2. Patient with active UC (Mayo  $> 2$ )
3. Pancolonic UC (colitis past the splenic flexure, Montreal E3))
4. Gastrointestinal surgery
5. Other GI diseases or systemic diseases (cardiac, renal failure, cirrhosis)
6. Shift work in the last 6 months
7. Antibiotic use within last 12 weeks
8. Patients who have used anti-diarrheal agents such as Lomotil or Imodium within 3 days of the study
9. Prednisone use the last 30 days
10. Significant Depression (score  $\geq 14$  BDI)
11. Significant Anxiety (score  $\geq 40$  STAI)
12. Use of probiotic supplement in last 4 weeks except yogurt.
13. Intentional change in diet.

14. Chronic use of NSAIDS. A washout period of 3 weeks is needed before the subject could be enrolled into the study. Low dose aspirin is allowed.
15. Chronic Alcohol use. A washout period of 3 weeks is needed before the subject could be enrolled into the study.
16. Have children under 6 months

**Subject Recruitment:** All Human UC subjects will be recruited at the RUMC Digestive Disease Clinic and the Rush Crohn's and Colitis Center by the PI or Clinical Coordinator. Healthy control subjects will be recruited by established recruiting methods, which we have successfully used over the past ten years, including notices to local organizations and internet, newspaper, and radio advertising. Based on our experience, of the initial calls made by potential subjects, 15% remain interested in the study after they are informed of study procedures. Of these individuals, 70% pass an initial telephone screening (in which questions are asked about medical condition, current medication use and work and travel history). Of those remaining individuals, 33% pass the medical and psychological screening (described below), and of these, 70% complete the study.

In this study we will recruit 40 Human Subjects in the following two groups:

- 1) Ulcerative Colitis (UC) (n=20).
- 2) Healthy Controls (HC) (n=20).

Each potential subject will undergo an extensive screening procedure prior to participation in the study. The procedure begins with a telephone screening, involving a series of questions from a preliminary screening questionnaire and answering any questions potential subjects may have about the study. If the original preliminary telephone screening questionnaire reveals no grounds for exclusion (see "Inclusion/Exclusion Criteria" below), then potential subjects are asked to come to our clinic for a physical examination. These patients will all be interviewed by the study Clinical Coordinator and then get a full physical exam by the PI who is a licensed Gastroenterologist. Potential subjects will also complete several questionnaires to determine their suitability for study. Each potential subject is given a tour of the Clinical Chronobiology Center (CCC) in which they will live during the temporal isolation portion of the study. Every attempt will be made to acquaint each prospective subject with all of the procedures involved in this study in order to minimize the possible effect of uncertainty about the experimental procedures on the results. Written informed consent on an RUMC IRB-approved form will be obtained from each subject before his/her study begins. Each subject will be told that they will be free to discontinue participation in the experiment at any time and that the investigators also reserve the right to discontinue the study for medical or other reasons at any time.

**Early Withdrawal:** Participants may withdraw at any time.

**Procedures:** After consenting for the study all subjects: 1) Will be interviewed by a study coordinator and fill out detailed questionnaires so that we can collect demographic data, medical history, data on disease status and research questionnaires; 2) Will supply blood and urine samples (to assess the inclusion/exclusion criteria and to obtain baseline biological markers; 3) Will undergo an exam by PI [name] to assess the inclusion/exclusion criteria and to obtain baseline UC disease characteristics and have initial blood drawn/urine sample. 4) After interviews and exam and blood/urine analysis, as part of the screening process, eligible patients will be asked to continue participation and will be re-informed about the study.

All experimental procedures will commence after admission to the CCC for a 7 day in-lab evaluation. The sleep episode will be the same as that maintained during the 2 weeks prior to the in-lab phase assessment. On Test Day 1 (TD1, Baseline alignment), at 0900h all subjects will have a unprepped flexible sigmoidoscopy (FS) with rectal biopsy collection (19 biopsies, ~15 cm from the anal verge), after which intestinal permeability will be assessed (24h urine collection after ingestion of a sugar cocktail: sucrose, mannitol, lactulose, sucralose103), and every 2 hour blood sampling during/surrounding standardized meals (primary and secondary outcomes for Specific Aims 1 & 2). During the last 8h of the phase assessment, subjects will be exposed to a background illumination ~3 lux to assess the endogenous circadian phase through hourly plasma melatonin (dim light melatonin onset, DLMO). On Protocol Day 3, subject behavioral cycles will be shifted by 12h, and this schedule will be maintained until Protocol Day 7. Following the short 4h sleep episode on Day 3, subjects will have 3 “night shift” days (Days 3-5). The 12h shift on Day 3 will be achieved by including an 8h wake episode and a 4h sleep opportunity, thereby maintaining the same sleep opportunity-to-wake ratio (1:2). The rationale for the 12h inversion of the sleep-wake timing is that we previously found that the influence of circadian misalignment on physiological variables are maximal when the sleep/wake and fasting/feeding cycle was shifted by ~12h relative to the endogenous circadian timing system. On Test Day 2 (TD2, Circadian misalignment), all subjects will have all the identical tests conducted as described on TD1; however, the FS and start of repeated measures will be at 2100 h – matched to the sleep/wake cycle and not clock time to isolate the impact of circadian misalignment. 24 hours prior to each flexible sigmoidoscopy, stool will be collected from subjects. Discharge from the lab will be on day 7 after an 8h sleep period. We will test for order effects (see Statistics).

**Blood draw.** Blood (30 cc) will be drawn in endotoxin free tube and serum then immediately separated and stored in -80°C freezer until measurement for Serum endotoxin (END). Blood will also be drawn for CBC, comprehensive biochemical profile [CMP that includes

liver function test], and PT. At first blood draw on Day 2 and last blood draw on Day 7, an additional 10 ml will be collected from patients on biologics, to evaluate antibody levels.

All subjects will complete an IBDQ, FFQ, BDI, STAI, PSQ, Munich Chronotype, IRLS, Demographic Questionnaire, Mayo Score, CSD-C (Consensus Sleep Diary), and Berlin Questionnaire. All information collected from subjects will be used for research purposes only. All the procedures in the study (blood draw, stool samples, urine samples, sigmoidoscopy with biopsies and questionnaires) are well-established and considered routine tests in clinical practice (including flexible sigmoidoscopy).

Diet Assessments: Meal habits will be recorded during screening. All subjects must eat breakfast (>200 kcal) at least 5 days a week, and subjects unusual diets by FFQ (vegan or gluten free) will be excluded due to impact on microbiota. For two weeks prior to each inpatient laboratory stay, all subjects will undergo ambulatory monitoring of their general activity using a small wrist activity monitor for ensuring compliance with the sleep-wake schedule. In addition, subjects will be provided meals for the last 3 days before admission and asked to keep regular meal schedules. Medical and psychiatric condition summary. Volunteers must be ambulatory and have no major visual or auditory handicaps. Medical suitability will be determined by clinical history, physical examination, and clinical biochemical screening tests of blood and urine, past or present psychopathology. Finally, a clinical interview will be carried out on all potential subjects to determine their suitability for the study and their ability to tolerate the conditions of the simulated night shifts environment (with regular contact with research staff and technicians). All volunteers selected must be drug-free with only moderate or no use of caffeine, alcohol, or other compounds by history, which will be verified during the screening process by comprehensive toxic analysis. Caffeine, alcohol, or other compounds (including herbal medications/remedies) will not be permitted for three weeks immediately prior to admission to the Clinical Chronobiology Center (CCC), and a urinary comprehensive toxic analysis will be carried out upon admission to ensure compliance. Prescribed medications are also prohibited with some exceptions.

[figure not shown]
Sleep Assessment: We will use a structured sleep questionnaire, the Pittsburgh Sleep Quality index, to access sleep habits. In addition, a Beck's depression index will be completed to evaluate a common confounder in sleep, depression. 2 weeks before participating in the circadian lab assessment, subjects completed sleep logs and wear a waterproof wrist actigraphy monitor (Actiwatch-L, Spectrum, Bend OR).

Phlebotomy: There may be some discomfort or bruising on the initial insertion of the catheter into a vein, but wearing the catheter should not be painful. Occasionally, mild discomfort may occur from the catheter in the vein. If this happens, it can be repositioned or removed, asking the subject's permission before any subsequent reinsertion. To help keep

the venipuncture site clean, we may ask permission to shave the forearm hair of the subject before insertion of the IV. There is a rare possibility of developing a small blood clot, inflammation, or local infection around the vein where the catheter is inserted, or in rare cases a generalized infection spread through the bloodstream as a result of the IV catheter. Occasionally, there is a black and blue mark at the site of the IV insertion, which may last a couple of weeks; and, rarely, a small scar may remain permanently at the venipuncture site.

**Saliva Collection:** Participants will be asked to produce a saliva sample on days 2-6 at 7 am and 7 pm. They will be provided a conical tube to spit into. A minimum of 2 ml is needed. To minimize contamination, participants will be instructed to not brush their teeth, use mouthwash, eat, or drink anything (except water) at least 1 hour prior to sampling. The tube of saliva will then be placed into a centrifuge and then aliquoted into 1.5 mL cryovials. One cryovial will have 500ul of saliva + 500ul of Zymo DNA/RNA 2x solution. The second cryovial will be 500ul of saliva flash frozen. These samples will be used for analysis of inflammatory cytokines and 16S sequencing. **Core temperature device:** On Day 2 and 5 participants will be given a Core device, a non-medical device that will measure their body core temperature. Body temperature will be used to measure the central circadian rhythm. The device will be programmed with the participant's study unique ID and it will be secured on their chest via medical grade adhesives when they get their catheter inserted on day 2 and 5. After activation, the device automatically collects and transmits core temperature data to our database. Once the day is completed the device will be removed from the participant's chest, the adhesive patches will be tossed out and the device will be disinfected.

**Flexible Sigmoidoscopy:** At two points in the study subjects will have an unprepped limited flexible sigmoidoscopy by [name] and sigmoid mucosal samples will be collected: 19 endoscopic pinch biopsy samples will be taken and used for: (a) two formalin-fixed and paraffin embedded for histology, (b) two OCT fixed for immunohistochemistry of AJC proteins, (c) two RNA Later for RT-PCR of AJC protein mRNA expression, (d) five snap frozen in liquid nitrogen for Western blot assessment of AJC proteins, (e) two snap frozen in liquid nitrogen for microbiota interrogation, and (f) six fresh samples to generate colonoids. Frozen samples will be transferred from liquid nitrogen tank to -80°C freezer within 8-12 hours.

**Data Collection:** All source data will be collected via a paper subject folder and/or a REDCap survey. Subject folders will be coded and stored in a locked cabinet within a locked research room only study staff will have access to. Data from the paper charts will be entered into the REDCap project for the study for electronic storage. The REDCap project is password protected on the Rush server and will only be accessible by IRB approved study staff.

**Biospecimen Collection & Storage:** All biospecimens collected for the purposes of this study will be coded and stored in the Rush Gastroenterology Research Laboratory. Only IRB approved study staff will have access to these samples.

**Data Analysis Methods:** 40 human subjects will be recruited into this proposed study: 20 Healthy Controls and 20 left sided UC subjects with inactive disease (Mayo Score  $\leq 2$ ) on stable mild to moderate medications (aminosalicylates, 5-ASA). All subjects (UC and HC) will be interviewed by the PI and will undergo a full medical history and physical examination including blood draw and urine collection. The PI is a licensed physician Gastroenterologist who specializes in the management of inflammatory bowel disease, to determine their eligibility and co-morbidities. Subjects who wish to participate will have the study explained by the coordinator and PI and will then sign a Rush IRB-approved informed consent. All UC subjects will complete a validated questionnaire regarding disease specific symptoms (Mayo Score) to determine they are inactive and may be enrolled in the study.

In addition, subjects will provide basic demographic data, UC history if appropriate, UC disease activity status as detailed further above, and Munich Chronotype questionnaire. All subjects will complete a validated 3 month food frequency questionnaires (FFQ) to collect dietary information (149). 40 participants (Specific Aims 1-2) will be enrolled for the within-subject prospective in-laboratory study protocols. Participants will be young (18-50 y), healthy,

non-diabetic, non-obese, Caucasian/African American/Asian and non-Hispanic/Hispanic in ratios consistent with the population of Chicago, and without medication use (excepting oral contraceptives) for HC. HC and UC subject will be matched according to age (  $\pm$  3 years), sex, race, and BMI (  $\pm$  3 kg/m^2). UC subjects will have only left sided disease, be on stable medications with no recent use of prednisone or antibiotics for the last 3 months. After signing an informed consent, subjects will fill out questionnaires start a food diary, and have 3 weeks of wrist actigraphy prior to their seven day in lab session in the Clinical Chronobiology Center (CCC). Since the participants will be in the sleep lab for 7 days, the questionnaire responses will be assessed for evidence of psychopathology, which is part of the exclusion criteria. [name], Ph.D., Associate Psychologist, will review the questionnaire responses before the participant finishes the screening. Participants who show some evidence of psychopathology on the questionnaires will undergo a structured interview (SCID-R) (~30 min) to confirm if they are ineligible.

**Subject Characteristics:** We will recruit (1) 20 HC subjects without any medical illnesses (2) 20 subjects with biopsy proven left sided UC, inactive (Mayo Score  $\leq$  2) on stable medications and no disease flares for > 3 months. HC and UC subject will be matched according to age (  $\pm$  3 years), sex, race, and BMI (  $\pm$  3 kg/m^2).

